### **Proportion of subjects who become transfusion independent**

The number and percentage of subjects with platelet or RBC transfusion independence during the study will be presented respectively. This analysis will be performed for the subgroup of subjects with baseline transfusion dependence.

Post-baseline transfusion independence is defined as follows:

- Platelet transfusion independence: The subjects who are transfusion dependent at baseline become transfusion free for a period of at least 4 weeks after baseline.
- RBC transfusion independence: The subjects who are transfusion dependent at baseline become transfusion free for a period of at least 8 weeks after baseline.

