8.3 Efficacy

Efficacy assessments include hematologic results, transfusion data, assessment of relapse and survival.

Hematologic parameters will be assessed at Screening, weekly from Week 1 to Week 8, then every 2 weeks to Week 26 (weekly until stabilization of the dose), then every 4 weeks until the end of eltrombopag treatment (every 2 weeks until stabilization of the dose) and yearly during the post-treatment follow-up (up to Year 3). Hematologic parameters will also be assessed as per the investigator decision to assess the maintenance of the response, relapse or for safety reasons.

Transfusion data will be recorded for any transfusion administered during the 60 days prior to treatment start and until the end of eltrombopag treatment for all participants who discontinue eltrombopag due to non-response at W26, relapse or alternative SAA treatment, and until the completion of study follow up for all the other participants. The date and time, content and number of units of each transfusion will be recorded.

Relapse will be determined according to the definition in this section by investigator and will be recorded into eCRF.

All participants will be followed for survival status every 3 months regardless of treatment discontinuation reason up to Year 3 until study completion, death, lost to follow-up, or withdrawal of consent for survival follow-up. Survival information can be obtained via phone, and information will be documented in the source documents and relevant eCRFs.

Hematologic response assessment will be performed by investigators at Week 13, Week 26, Week 52 and yearly after. At Week 13 and Week 26, responses assessment needs to be confirmed by two serial blood count measurements performed 1-3 weeks apart.

Response is defined as blood counts no longer meeting the standard ("Camitta") criteria (Camitta et al 1975) for severe pancytopenia in SAA, equivalent to 2 of the following values (Scheinberg et al 2009).

- Absolute neutrophil count $\geq 0.5 \times 10^9/L$
- Platelet count $\geq 20 \times 10^9/L$
- Reticulocyte count $\geq 20 \times 10^9/L$

A CR will be defined as (all 3 must be met):

- Absolute neutrophil count $> 1.0 \times 10^9/L$
- Platelet count $> 100 \times 10^9/L$
- Hemoglobin $> 100 \text{ g/L}$

A PR will be defined as blood counts that do not meet criteria for SAA but are not sufficient for a CR.

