Improvement in counts that are dependent upon exogenously administered growth factors or transfusion will not be considered as fulfilling response criteria.

The exclusion period of these therapies are detailed below:

- Platelet transfusions: 7 days preceding the assessment of platelet count
- Packed RBC transfusions: 14 days preceding the assessment of hemoglobin
- Growth factors: 21 days preceding the assessment of response

No response (NR) is defined as not fulfilling the response criteria.

Transfusion independence at each assessment point is defined as follows:

- Platelet transfusion independence: The participants who are transfusion dependent at baseline become transfusion free for a period of at least last 4 weeks.
- RBC transfusion independence: The participants who are transfusion dependent at baseline become transfusion free for a period of at least last 8 weeks.

Clinical relapse is considered as the occurrence of any of the following event in a participant who had achieved a hematological response (CR or PR) but has subsequently lost response (not explained by any other independent concomitant medical conditions):

- meeting again the criteria for SAA
- requirement for transfusion again for participants who had been transfusion independent
- decrease in any of the peripheral blood counts to: absolute neutrophil count $< 0.5 \times 10^9/L$ or platelets $< 20 \times 10^9/L$.

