The number and percentage of participants with platelet or RBC transfusion independence at any time during the study will be presented respectively. This analysis will be performed for the subgroup of participants with baseline transfusion dependent.

Overall survival

OS is defined as the time from the date of the first dose of study treatment to the date of death due to any cause. If a participant is not known to have died, survival will be censored at the date of last contact. The distribution function of OS will be estimated using the Kaplan-Meier method and will be plotted. OS rate will be estimated at Week 26, Week 52 and yearly after as well.

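### Both SAPs drop the assessment-point anchor from the protocol's definition of transfusion independence, so a single 4- or 8-week gap anywhere after baseline can count, and the change is not declared

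*SAP*

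**What the plan says.** Protocol 8.3 introduces the definition with "Transfusion independence at each assessment point is defined as follows". For platelets it reads "The participants who are transfusion dependent at baseline become transfusion free for a period of at least last 4 weeks", and for red cells "The participants who are transfusion dependent at baseline become transfusion free for a period of at least last 8 weeks". The same section fixes the response assessments: "Hematologic response assessment will be performed by investigators at Week 13, Week 26, Week 52 and yearly after". Protocol 12.5.1 gives the summary rule, restricted to participants who were dependent at baseline: "The number and percentage of participants with platelet or RBC transfusion independence at any time during the study will be presented respectively".

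Section 2.7.1 of the primary-analysis SAP defines post-baseline independence for platelets as "Platelet transfusion independence: The subjects who are transfusion dependent at baseline become transfusion free for a period of at least 4 weeks after baseline", with 8 weeks in place of 4 for red cells. The final-analysis SAP repeats this. Section 2.7.2 of both SAPs keeps the protocol's any-time summary. Section 4 of each SAP lists only added endpoints, and neither document history mentions a changed definition of independence. The endpoint is not among those that Section 2.7 of the final-analysis SAP says will not be reproduced.

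**The concern.** Two elements of the protocol definition are missing from the SAPs: the tie to an assessment point, and the word *last*. Under the protocol the question is whether the participant is free of transfusion when assessed. Under the SAPs it is whether the participant was ever free for 4 or 8 weeks, at any moment after baseline.

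The denominator makes this matter. Under Protocol 8.2, one platelet transfusion in the 4 weeks before Day 1, or one red-cell transfusion in the 60 days before, is enough for baseline dependence. An irregular pattern with no change in need can then produce a qualifying gap by chance. The trial has no control arm to show how often that happens, so the reported proportion would be hard to interpret as an effect on the need for transfusion.

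There are two connected effects. First, SAP 2.7.1 derives relapse by program, and one of its triggers is a renewed need for transfusion in someone who had been independent. Second, Protocol 6.2.1 and 8.3 stop recording transfusions at the end of eltrombopag for participants who discontinue it because of non-response at Week 26, relapse or alternative treatment. The SAPs set no end to the transfusion-free period, so unrecorded time could be read as a gap.

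**Working it through.** The plan states no expected rate or precision for this endpoint, so there is no figure of its own to reproduce.

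**Inputs from the documents.** Required gap G = 28 days (platelets) or 56 days (red cells), from Protocol 8.3 and SAP 2.7.1. Week 13 is Day 92 and Week 26 is Day 183, from Protocol Table 8-1.

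**Rules.** Let a participant's transfusion days in (0, 183] be t1 < … < tk, with t0 = 0 and t(k+1) = 183.
- SAP rule: counted if the largest t(j+1) − t(j) is at least G.
- Protocol rule at visit v: independent if no transfusion falls in (v − G, v]. For the any-time summary to Week 26, counted if this holds at v = 92 or v = 183.

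A participant who meets the protocol rule at a visit has a free stretch of at least G ending there, so also meets the SAP rule. The converse fails. The SAP proportion can never be the lower one.

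**Constructed calendars, Days 1–183.**
- Platelets weekly, with one pause from Day 21 to Day 56 (35 days), 22 transfusions: independent under the SAP, at neither visit under the protocol.
- Platelets every 30 days throughout: independent under the SAP, at neither visit under the protocol (transfused on Days 90 and 180).
- Red cells every 14 days, with one pause from Day 98 to Day 168 (70 days): independent under the SAP, at neither visit under the protocol.
- Platelets every 7 days, or red cells every 14 days, without a pause: independent under neither rule.

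**Simulation.** The documents give no transfusion frequencies, so every rate here is an assumption. Intervals between transfusions are gamma distributed with a constant mean and no treatment effect, 40,000 participants per setting. Shape 1 is fully random timing, shape 4 moderately regular, shape 16 near-regular. Entries are SAP rule versus protocol rule (met at Week 13 or Week 26), in %.

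| Product, mean interval | Shape 1 | Shape 4 | Shape 16 |
|---|---|---|---|
| Platelets, 7 days | 36.8 vs 3.8 | 0.2 vs 0.0 | 0.0 vs 0.0 |
| Platelets, 14 days | 90.8 vs 25.4 | 40.4 vs 3.0 | 0.7 vs 0.0 |
| Platelets, 21 days | 98.6 vs 45.9 | 90.9 vs 17.0 | 56.2 vs 2.8 |
| Red cells, 14 days | 18.0 vs 3.5 | 0.1 vs 0.0 | 0.0 vs 0.0 |
| Red cells, 28 days | 64.4 vs 25.2 | 20.0 vs 2.8 | 0.3 vs 0.0 |
| Red cells, 42 days | 84.9 vs 46.2 | 63.4 vs 17.1 | 29.2 vs 3.1 |

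Over all settings run (means 7 to 30 days for platelets, 14 to 60 for red cells), the excess ranges from 0 to about 75 points; the largest is platelets, mean 30 days, shape 16: 99.7 − 24.9 = 74.8. These runs did not condition on baseline dependence. A separate run that did (look-back 28 days for platelets, 56 for red cells) gave nearly the same SAP-rule figures: 90% and 40% for platelets at 14 days with shapes 1 and 4, and 64% and 20% for red cells at 28 days.

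**The case against.** The strongest reply is that the any-time summary is the protocol's own (12.5.1), and that 8.3 does not define an assessment point. Weeks 13, 26, 52 and yearly are named there for the hematologic response assessment, while Table 8-1 records transfusions at every treatment visit. If every scheduled visit is an assessment point, the two rules come closer. Repeating the simulation on that reading gives, for platelets at a 14-day mean, 90.1% against 77.1% with random timing and 40.6% against 18.2% with shape 4; for red cells at a 28-day mean with random timing it gives 64.3% against 55.7%. The reading narrows the excess but does not remove it, and it does not restore the missing word *last*.

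Other planned outputs are anchored to visits: the transfusion-free interval before Weeks 13 and 26, and transfusion frequency and amount in the 4 or 8 weeks before each visit. They help show whether need persists, but the reported category combines a decrease with being transfusion free, so none of them tabulates independence by visit.

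Four stronger readings are tempting, and the documents do not support them:
- **Regularly transfused participants count as independent.** They can count only if they have at least one gap of 28 or 56 days. Near-regular timing at the shorter mean intervals gives figures close to zero.
- **The SAP is what lets Week 26 non-responders count.** Under 8.3 with 12.5.1, a participant free at Week 13 and a non-responder at Week 26 already counts.
- **The fair comparator is Week 26 alone.** That would set 90.8% against 13.4% for platelets at 14 days with random timing, roughly doubling the ratio (6.8 instead of 3.6), but it ignores the any-time rule.
- **The discrepancy grows to Year 3 for non-responders.** Their transfusions are not recorded after eltrombopag ends, so there are no data for this.

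**Conclusion.** The point holds. The SAPs' definition is looser than that of Protocol 8.3, the change is undeclared, and someone who is independent at no assessment point can be reported as having become independent. How many participants this affects cannot be taken from the documents. Under the assumed rates, the effect runs from none (frequent, near-regular transfusion) to most of the dependent group (irregular or less frequent transfusion). The figures rest on a constant need, no treatment effect, follow-up to Week 26, and Weeks 13 and 26 as the assessment points.

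The consequence is limited. This is a descriptive secondary endpoint with no test attached, and the primary complete-response analysis does not use it. The relapse derivation is touched only among responders, because relapse requires an earlier complete or partial response. There a looser status can only add relapses, which would shorten the duration of response. A reader might infer that it flatters that endpoint, but the definitions point the other way.

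**What to change.** In Section 2.7.1 of both SAPs:
- Restore the Protocol 8.3 definition: no platelet transfusion in the last 4 weeks, or no red-cell transfusion in the last 8 weeks, before the assessment.
- Report n (%) independent at Weeks 13, 26, 52, Year 2 and Year 3 among participants dependent at baseline. For the any-time figure, count a participant who meets the definition at one or more of these points.
- Stop counting transfusion-free time at the end of transfusion recording for that participant.
- Use the same status in the programmed relapse derivation.
- Keep any 4- or 8-week gap after baseline only as a labelled supplementary summary, and declare it in Section 4.

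The cost is SAP wording and one table by visit, from transfusion dates already collected. The reported proportion is likely to fall. After Week 52 the assessments are a year apart, so independence that falls only between late visits will appear only in the supplementary summary, which is the reason to keep it.

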### **Transfusion frequency and amount (units)**

For subjects receiving platelet transfusion at baseline, the frequency and the amount of platelets transfusion in each period (Baseline: 4 weeks before Day 1; Week 13, 26, 52 and Yearly

thereafter: 4 weeks before each visit day) will be summarized. The same analysis applies to RBC transfusion (period will be extended to 8 weeks). The amount of transfusion will be defined as the sum of units of transfusion.

Subjects with platelet transfusion decrease is defined as subjects with transfusion decrease or transfusion free in each period (Week 13, 26, 52 and Yearly thereafter: 4 weeks before each visit day) compared to baseline (Baseline: 4 weeks before Day 1). 50% platelet transfusion reduction is defined as subjects with transfusion decrease of amount (units) at least 50% compared to baseline. The same analysis applies to RBC transfusion (period will be extended to 8 weeks). The number and percentage of subjects with platelet or RBC transfusion decrease and 50% platelet transfusion reduction in each period will be presented.

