6.2 Other treatment(s)

6.2.1 Concomitant therapy

All medications (including non-prescription drug and herbal medicines), procedures, and significant non-drug therapies (including physical therapy and blood transfusions) administered after the participant was enrolled into the study (after signing the ICF) must be recorded in the concomitant medications/significant non-drug therapies or procedures pages on the case report forms (CRFs):

- Drug for aplastic anemia other than r-ATG and CsA (G-CSF, iron chelation therapy and supportive therapy except transfusions): from 7 days before the start of administration of the investigational product (or from the screening visit, whichever is earlier) to completion of study;
- RBC and platelet transfusion: from 60 days before the start of administration of the investigational product to the end of eltrombopag treatment for participants who discontinue eltrombopag due to non-response at W26, relapse or alternative SAA treatment, and until the completion of study for all the other participants;
- All concomitant therapy other than the above-mentioned: up to the resolution of the last reported AE.

Transfusions with platelets and/or RBC may be given during study participation as medically necessary per local practice. In general, platelet transfusions should be administered prophylactically when the platelet count $<10 \times 10^9/L$ or when significant bleeding occurs. Prior

to administration of r-ATG, a daily threshold of $20 \times 10^9/\text{L}$ should be used for the duration of the r-ATG course. In participants judged to have additional risk factors for bleeding, a higher prophylactic transfusion threshold of $20 \times 10^9/\text{L}$ is also recommended. Packed RBCs are recommended generally to be administered for hemoglobin $<60 \text{ g/L}$, and it should be individualized according to co-morbidities. Improvement in counts that are dependent upon transfusion will not be considered as fulfilling response criteria in the efficacy assessments (see [Section 8.3](#)).

The use of antibiotics (except for macrolide antibiotics, which may increase the concentration of CsA, mentioned in [Section 6.2.1.1](#)), anti-fungals, and granulocyte colony stimulating factor (G-CSF) are permitted. The local hospital guidelines for treatment of infections / febrile neutropenia should be followed. Cautions should be taken when azole anti-fungals are administered, mentioned in [Section 6.2.1.1](#).

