PK blood sampling				Intensive PK in 12 Chinese adult participants and all Japanese pediatric participants (pre-dose, 2, 4, 6, 8, and 24 h post-dose) on day 14 after initial dose; Sparse PK in all participants: Pre-dose on day 15 after initial dose and pre-dose on day 15 after each new dose has started (dose reduction only)															
Hematological response assessment												X	X		X	X		X ²	
Survival follow-up			All participants will be followed for survival status every 3 months regardless of treatment discontinuation reason until study completion (Year 3), death, lost to follow-up, or withdrawal of consent for survival follow-up.														X		
Treatment compliance			S	S	S	S	S	S		S		S	S	S	S	S	X ² (S)	X ² (S)	
Disposition	X											X		X	X	X		At Year 3	
Prescription of eltrombopag		X	X	X	X	X	X	X	X		X	X	X	X					

Period	Screening	Core treatment part											Extension part		EOT		Long-term Follow-up	
		Day 1	Week 1	Week 2	Week 3 / 5 / 7	Week 4 / 8	Week 6	Week 9/11/15/17/19/21/23/25 when dose adjusted	Week 10/12/14/16/18/20/22/24	Week 13	Week 26	Week 28 to Week 50 ¹	Week 52	End of treatment	Safety follow-up	Survival follow-up	Year 2 / Year 3	
Visit Name	Screening																	
Days	-30 to -1	1	8	15	22 / 36 / 50	29 / 57	43	64 to 176	71 to 169	92	183	197 to 351	365	EOT	30 days after EOT	every 3 months	729 / 1093	
Prescription of r-ATG		Administered intravenously on Days 1 to 5																
Prescription of CsA		X	X	X	X	X	X	X	X	X	X	X	X	X	X ²	Monthly up to Year 2 ²		

^X Assessment to be recorded in the clinical database or received electronically from a vendor
^S Assessment to be recorded in the source documentation only
¹ Participants should visit hospital at least every 2 weeks until stabilization of dose; every 4 weeks after stabilization of dose.
² For participants that discontinue eltrombopag due to reasons other than non-response at W26, relapse or alternative SAA treatment
³ At Screening or Day 1
⁴ For participants who discontinue eltrombopag treatment prior week 26 or at visit week 26 a serum test is required at both visits. For participants who discontinue eltrombopag during extension part (week 28 to 50) or at visit week 52 a urine test is required at EOT only and serum test at the safety follow up visit.

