8.4.4 Evaluation of clonal evolution

Cytogenetic abnormalities will be assessed during the whole study. For all participants, regardless of disposition, the assessments will be monitored at Week 13, Week 26, Week 52 and yearly after, and when clinically indicated.

Cytogenetic abnormalities will be assessed by karyotyping (G-banding) and FISH (for example, probes targeting abnormalities in chromosome 3, 5, 7, 8 and those associated with SAA, MDS, AML etc).

Detection of PNH and measurement of PNH granulocyte clone size measurement by flow cytometry will be done at screening period. If persistently negative, it will be monitored every 6 months up to Year 2 (Week 104) and then Year 3 (Week 156) unless symptoms or signs develop. If the PNH screen is, or becomes positive, it will be tested every 3 months and only reduce the frequency if the proportion of the PNH cells has remained stable ([Killick et al 2016](#)).

Clonal evolution to AML and MDS will also be monitored during the study period, and relevant examinations will be done when clinically indicated.

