9.1 Discontinuation

9.1.1 Discontinuation of study treatment

Discontinuation of study treatment for a participant occurs when study treatment is permanently stopped earlier than the protocol planned duration and can be initiated by either the participant or the investigator.

The investigator must discontinue study treatment for a given participant if, he/she believes that continuation would negatively impact the participant's well-being.

Study treatment must be discontinued under the following circumstances:

- The hematologic response is assessed as NR at Week 26.
- Diagnosis of relapse.
- Participant/guardian decision.
- Pregnancy.
- Any of the following is observed: a new clinical significant morphological, chromosomal or cytogenetic abnormality*, diagnosis of myelofibrosis^{**} or progression to MDS or AML.
- Participant meets any of the stopping criteria in [Section 6.5.1](#).
- Any laboratory abnormalities that in the judgment of the investigator, taking into consideration the participant's overall status, prevents the participant from continuing the study treatment.
- Use of prohibited treatment as per recommendations in the prohibited treatment section (see [Section 6.2.2](#)).
- The participant is withdrawn from the treatment with planned r-ATG or CsA, or the participant cannot tolerate the planned study treatment (e.g. Infusion-related r-ATG reactions refractory to all appropriate supportive measures; Life threatening acute hypersensitivity reactions).
- The participant has an unacceptable AE whose causal relationship with eltrombopag cannot be ruled out.
- The participant is found to be significantly non-compliant with the requirements of the protocol (including treatment non-compliance).
- The investigator (or sub-investigator) believes that the participant will not benefit from eltrombopag or
- that the participant needs to transfer to other therapy (e.g. HSCT, ATG/ALG).
- The study is prematurely terminated.
- Any situation in which study participation might result in a safety risk to the participant.

*: Discontinuation should be considered if any new chromosomal or cytogenetic abnormality is observed, and if considered significant should be discontinued. This also applies for participants that started treatment based on normal karyotyping while FISH results were not yet available.

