### **Transfusion frequency and amount**

The transfusion frequency and amount and the proportion of subjects with transfusion decrease will be only performed for the subgroup of subjects with baseline transfusion dependent.

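### Transfusion outputs at Week 52 and later, and transfusion independence, are scored over periods in which some treatment failures are no longer recorded

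*SAP*

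**What the plan says.** **Collection.** Protocol 6.2.1 records RBC and platelet transfusions "to the end of eltrombopag treatment for participants who discontinue eltrombopag due to non-response at W26, relapse or alternative SAA treatment". Everyone else stays under collection for longer, as the same bullet goes on to state: "and until the completion of study for all the other participants". Protocol 8.3 repeats the rule: "until the end of eltrombopag treatment for all participants who discontinue eltrombopag due to non-response at W26, relapse or alternative SAA treatment". Footnote 2 to Table 8-1 agrees. It limits transfusion recording in long-term follow-up as follows: "For participants that discontinue eltrombopag due to reasons other than non-response at W26, relapse or alternative SAA treatment". Protocol 9.1.1 makes stopping study treatment mandatory in several circumstances, including "The hematologic response is assessed as NR at Week 26" and a diagnosis of relapse.

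**Scoring.** Section 2.7.1 of the primary-analysis SAP, repeated in the final-analysis SAP, summarises transfusion frequency and units at Week 13, 26, 52 and yearly. The look-back from the visit day is 4 weeks for platelets and 8 weeks for RBC. It then defines a decrease: "Subjects with platelet transfusion decrease is defined as subjects with transfusion decrease or transfusion free in each period". A 50% reduction in units is scored over the same periods. Section 2.7.3 adds one restriction, that the analysis "will be only performed for the subgroup of subjects with baseline transfusion dependent".

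Transfusion independence means at least 4 transfusion-free weeks (platelets) or 8 (RBC) after baseline, and is reported if it occurs at any time during the study (SAP 2.7.1 and 2.7.2).

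**Later visits.** Participants who fail keep later study visits for clonal evolution (Protocol 8.4.4): "For all participants, regardless of disposition, the assessments will be monitored at Week 13, Week 26, Week 52 and yearly after".

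**The concern.** Transfusions are event records. Once recording stops, a transfused participant and an untransfused one look the same in the database. The SAP definition tests for the absence of transfusions in a window but not whether anyone was recording them.

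The participants affected are not a random subset. Recording ends because they did not respond, relapsed or moved to another SAA treatment. Renewed need for transfusion is itself one of the relapse criteria in Protocol 8.3, so for a participant who relapses on eltrombopag the return of that need can be what ends the recording.

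Less need for transfusion is among the expected benefits in Protocol 4.5. The final-analysis SAP (2.7) does not reproduce the Week 13 and Week 26 transfusion frequency and amount outputs, so the periods it newly reports, Week 52 and yearly, are the exposed ones.

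**Working it through.** **The plan's own figures.** The documents give no expected value for any transfusion outcome. Their only sizing figures are the exact 95% intervals for 36 participants (Protocol Table 12-2, SAP Table 3-1). These reproduce: 14/36 gives 23.1-56.5, 16/36 gives 27.9-61.9, 18/36 gives 32.9-67.1, and the maximum half-width is 17.1%. They do not bear on this point.

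**Step 1: place the windows on the calendar.** Table 8-1 puts Week 26 at Day 183 and Week 52 at Day 365.
- Platelet look-back at Week 52 starts at 365 - 28 = Day 337.
- RBC look-back at Week 52 starts at 365 - 56 = Day 309.
- A Week 26 non-responder stops eltrombopag at about Day 183, so both windows lie wholly after recording ended. The same holds at Year 2 (Day 729) and Year 3 (Day 1093).
- For independence, the first 28 unrecorded days run to about 183 + 28 = Day 211 and the first 56 to about 183 + 56 = Day 239. Either could be read as a qualifying transfusion-free spell.

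**Step 2: look for a rule that closes the gap.**
- SAP 2.7.3 treats non-evaluable participants as non-responders, but only for CR and overall response rates.
- SAP 2.1 uses the whole population or subgroup as the denominator, with a missing category where applicable. Nothing defines an unrecorded transfusion window as missing.
- Protocol 9.1.1 asks for new and concomitant treatments after discontinuation, but the transfusion-specific rule in 6.2.1 and 8.3 is narrower.

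**Step 3: size, as an illustration.** Let D be the number dependent at baseline, F those whose recording has ended, d those with a decrease among the D - F still recorded, and t the number of F who truly had a decrease.
- True proportion: (d + t)/D
- Unrecorded read as transfusion free: (d + F)/D
- Unrecorded dropped: d/(D - F)
- Unrecorded kept as not decreased: d/D

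Assumptions not in the documents: D of 24, 30 or 36; F of 30%, 43% or 50% of D; d of 90% of those recorded; t from 0 to 50% of F. Counts are rounded to whole participants. The 43% corresponds to 3 of 7 not responding in the Japanese study (Protocol 4.5).

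Worked case, D = 30, F = 13, so 17 recorded and d = 15:
- Read as transfusion free: (15 + 13)/30 = 93.3%
- Dropped: 15/17 = 88.2%
- Kept as not decreased: 15/30 = 50.0%
- True: 15/30 = 50.0% (t = 0) to 21/30 = 70.0% (t = 6)

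| Handling | Range over the grid | Excess over true |
|---|---|---|
| True | 16/36 = 44.4% to 19/24 = 79.2% | none |
| Read as transfusion free | 33/36 = 91.7% to 29/30 = 96.7% | 22/24 - 19/24 = 12.5 points, to 29/30 - 14/30 = 50 points |
| Dropped | 22/25 = 88.0% to 14/15 = 93.3% | 15/17 - 19/24 = about 9 points, to 14/15 - 14/30 = about 47 points |
| Kept as not decreased | 16/36 = 44.4% to 19/30 = 63.3% | zero or below |

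**The case against.** **The SAP states neither favourable outcome.** The visit day that anchors each window is undefined. Efficacy assessments end at Week 26 non-response, relapse or alternative treatment (Protocol 3, 8 and 9.1.1), and Protocol 8.4.4 continues only clonal assessments. If the visit day means an efficacy visit, these participants have no late window. With the denominator convention in SAP 2.1 they could then stay in the denominator uncounted, which gives the same proportion as the handling proposed here. This stands as a possible reading, so it is wrong to say that the SAP instructs failures to be scored as successes. But the reading is not stated for transfusion windows. It does nothing for the means and medians of frequency and units, or for independence at any time.

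**Not exactly the failures.** A reader might infer that recording stops for exactly the participants who fail. It does not. The stop depends on the reason for discontinuing eltrombopag. Someone who completes eltrombopag at Week 52 and relapses later, or who stops for another reason and then fails, is still recorded to study completion.

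**Not 43 to 50 points.** A reader might also take the non-response figures in the protocol (3/7 = 42.9%, or 15.4 of 36; about half in the Chinese registry, or 18 of 36) as the inflation itself. That is an upper bound. It needs all 36 to be dependent at baseline, every non-responder to have stopped recording and to have a later visit, and none to have truly decreased. The registry treated without eltrombopag, and the seven-participant study also enrolled moderate disease. Neither is an expectation for this trial.

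**Reach.** The decrease endpoint was added by the SAP (section 4) and is supportive. Week 13 and Week 26 results are largely unaffected.

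**Conclusion.** The mismatch is real: both SAPs score windows that the protocol does not collect, selectively for participants whose treatment has failed. Following the written definition can give a wrong result, and leaving these participants out gives a result mainly in responders. Both errors favour the treatment.

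The size cannot be fixed from the documents, because baseline dependence, the share with recording stopped and the true decrease among failures are all unknown. Under the stated assumptions the late decrease proportion is overstated by about 12 to 50 points if unrecorded windows are read as transfusion free, and by about 9 to 47 points if these participants are dropped. The effect on independence was not quantified.

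The point is confined to the supportive transfusion outputs at Week 52 and later and to transfusion independence, a protocol secondary endpoint. The primary CR rate does not depend on it. It should be corrected, but it does not threaten the main conclusion.

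**What to change.** In both SAPs:

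1. Let only days under transfusion collection count toward transfusion-free status, decrease, 50% reduction and independence.
2. For the Week 52 and yearly proportions, keep all baseline-dependent participants in the denominator. Count those whose collection ended for non-response, relapse or alternative SAA treatment as not decreased and not transfusion free, in line with the non-responder handling in 2.7.3.
3. For independence, require the 4 or 8 transfusion-free weeks to lie wholly within the collection period.
4. Show the number under collection beside each frequency and units summary, and label those summaries as limited to participants still under collection.

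The cost is a few sentences of SAP text and a programming flag from the discontinuation reason already collected. No new data are needed. The late proportions become less favourable, and item 2 is conservative for failures who truly had a decrease: in the illustration it understates the true proportion by at most 22/30 - 14/30 = about 27 points. Item 4 does not recover the missing units; it only makes the limitation visible.
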